### 3.4b. Mood Measures

We may of mood and anxiety at intake and also on the PET scan day including the following.

1. Center for Epidemiological Studies Depression Scale (CES-D) The CES-D (149) is a 20-item self-report instrument, which has been extensively used in both clinical and nonclinical populations to measure the frequency and severity of depressive symptoms over the past week. The CES-D, which has been used to document the severity of depressive symptoms in adults (150) and has been shown to be a sensitive measure of negative affect in smokers (151), will be used in the proposed studies to exclude for presence of major depression, and to measure level of mild depressive symptoms commonly noted in tobacco smokers.
2. Anxiety: The State-Trait Anxiety Inventory (152) is a 40-item, self-report measure, comprised of two subscales. The State-Anxiety scale is 20 items and assesses transitory states characterized by feelings of tension, apprehension, and heightened autonomic reactivity. The Trait-Anxiety scale is 20 items and assesses stable individual differences in anxiety proneness.
3. Impulsivity: Barratt Impulsiveness Scale (BIS; (153)) is a 30 item self-report instrument designed to assess the personality/behavioral construct of impulsiveness.

### 3.4c. Smoking Measures

We may obtain smoking measures at intake and also on the PET scan day, which may include the following.

1. Fagerstrom Test for Nicotine Dependence (FTND).(154) This will be used to measure the severity of nicotine dependence. It is a 6-item scale with an internal consistency of .61 and its total score is closely related to biochemical measures of intensity of smoking. A score of at least 3 is necessary for inclusion in the study.
2. Smoking History. This questionnaire will assess basic smoking status and history such as number of years smoked, number and length of quit attempts, reasons for quitting, and second hand smoke exposure.
3. Nicotine Withdrawal Checklist.(155) This measures the severity of eight withdrawal symptoms on 5-point Likert scales.
4. Tiffany Questionnaire of Smoking Urges (QSU).(156) The QSU-brief is a 10-item questionnaire that evaluates the structure and function of smoking urges. Subjects indicate on a likert-type scale how strongly they agree or disagree with each statement with a score of 1 (strongly agree) to 7 (strongly disagree). This characterizes ‘urges to smoke’ into a negative affect related to relief of withdrawal symptoms and positive affect related to expectancy of reinforcement.
5. GLMS – set of questionnaires in which subjects rate sensations related to smoking such as craving on a scale from “no sensation” to “strongest imaginable.”
6. LHS – set of questionnaires in which subjects rate hedonic reaction to sensations from smoking on a scale from “most disliked sensation imaginable” to “most liked sensation imaginable.”

### 3.4d Cognitive Measures

We may obtain these measures at baseline and up to two times on the PET days.

**1. Cogstate Battery (30 minutes)** – This computerized test battery will assess memory and cognition. The tasks may include:

- a. International Shopping List Task – a computerized task to assess verbal learning and memory.
- b. Groton Maze Learning Task – a computerized task to assess executive function and spatial problem solving.
- c. Detection Task – a computerized task to assess psychomotor function and speed of processing.
- d. Identification Task – a computerized task to assess visual attention and vigilance.
- e. One Card Learning Task – a computerized task to assess visual learning and memory.
- f. One Back Task – a computerized task to assess attention and working memory

**2. Probabilistic Reward Task:** The PRT has been successfully used to assess reward responsiveness (166-168). In each trial, subjects choose which of two difficult-to-differentiate stimuli was presented. Stimuli consist of simple cartoon faces (diameter: 25 mm; eyes: 7 mm) presented in the center of the monitor. At the beginning of the trial, the face has no mouth. After a given delay, either a straight mouth of 11.5 mm (“short mouth”) or 13 mm (“long mouth”) is presented for 100 ms. Subjects are instructed to press an appropriate button to decide whether a long or small mouth had been presented. Unbeknownst to subjects, correct identification of one stimulus (“rich stimulus”) is rewarded three times more frequently (“*Correct! You won 20 cents*”) than the other (“lean”) stimulus. In healthy controls, this reinforcement schedule leads to a response bias (i.e., a preference for the more frequently rewarded stimulus). The degree of response bias toward the more frequently reinforced alternative will be used for operationalizing sensitivity to reward.

**3. Conditioned Hallucinations Task:** participants’ thresholds for detection (75% likelihood of detection) of a tone embedded in white noise will be determined using the maximum-likelihood-based QUEST62 method, with detection and non-detection signaled by button-press. Target auditory stimuli will be of the following easily-discernible frequencies: 500, 1000, 1500, 2000, and 2500 Hz. All target auditory stimuli will be paired with a unique visual pattern (colors: white, blue, orange, red, green, matched for luminance and contrast) present for the duration of the auditory stimulus presentation. All auditory and visual stimuli will be randomized across participants and across assessments. Given participant responses, individualized psychometric functions will be estimated, corresponding to likelihood of detection as a function of target stimulus intensity, and from this, estimations of the intensities at which individuals will report detection of the target stimulus at rates of 50% and 25% will be determined. Over twelve blocks, participants will be presented first with stimuli played at their detection threshold, and then increasingly with sub-threshold and absent stimuli. This is meant to foster implicit learning and subsequent testing of the association between light and tone. Participants will respond by button-press, and during the train/test period will hold down response buttons to indicate degree of confidence in their answer, guided by an on-screen visual-analog scale. Conditioned Hallucination trials will be taken to be those during which participants report the presence of the target tone despite its absence.

#### 4. Cold Pressor Task

Subjects may be asked to participate in the Cold Pressor Task. The cold pressor task (CPT) is a stress task used to measure pain sensitivity and pain tolerance. This task will be used to determine alterations in pain thresholds as a result of nicotine use. Participants will immerse their hand (up to the wrist) for up to 3 minutes in the experimental (ice-cold temperature 0-4°C) and control (room temperature (20°C)) conditions. Physiological measure (heart rate, blood pressure and subject responses (stress, mood) will be collected 5 minutes before, 1 minute into, and immediately after the CPT.

#### 3.4.e Schizophrenia assessments

Scale for the Assessment of Negative Symptoms (SANS), the Positive and Negative Symptom Scale (PANSS), the Abnormal Involuntary Movements Scale (AIMS), the Montgomery-Asberg Depression Scale (MADRS) for depression to assess any mood or behavioral changes

### 3.5 Experimental Methods

#### MRI.

Within approximately 6 months of the PET study, anatomical MRIs will be acquired at the Yale University MRI Center. Subjects will be taken through a ferromagnetic metal detector before entering the scan room. The purpose of the MRI scan is to direct the region of interest placement on the lower resolution PET images. The T1 weighted images will be acquired on a 3 Tesla Siemens Scanner. There will also be an additional resting state scan with subjects in the scanner, eyes open, fixating on a cross. Smokers who participate in Aims 4 and 7 may return for a second MRI with resting state at 4-8 weeks of smoking abstinence.

#### Physostigmine challenge (same paradigm as HIC# 09100005837)

Physostigmine will be administered as follows. Glycopyrrolate, a cholinergic antagonist that does not have central side-effects, will be administered prior to physostigmine challenge to block physostigmine peripheral side-effects (e.g. nausea). Subjects will receive 200 mcg /ml x 1 ml of glycopyrrolate through an IV. Physostigmine administered i.v. has a short half life of 20 min with peak plasma levels 20-30 min post administration. The same dose of physostigmine will be administered as in the preliminary data: 1.5 mg/hr for 1 hr. Vital signs, including systolic and diastolic blood pressure, heart rate and respiration rate, will be monitored before physostigmine and then at 10, 20, 30, 60 min after the beginning of the infusion and then hourly until the end of the study day. Subjects will be questioned before, during, and after physostigmine challenge about potential adverse reactions typical to this medication (nausea, upset stomach, etc., as in Risks section). [If there is a significant and persistent drop in subjects' heart rate (>15% for at least 1 min), the IV physostigmine infusion will be stopped but the subject will continue to be monitored and will be discharged at the discretion of the study doctor. In emergency situation, PET center protocol will be followed accordingly (on file with HIC).

#### Amphetamine challenge

Dextroamphetamine sulfate is the dextro isomer of the compound d,l-amphetamine sulfate, a sympathomimetic amine of the amphetamine group. It is an FDA approved drug available for the treatment of narcolepsy and attention deficit hyperactivity disorder (maximum approved total

daily dose of 5-60 mg). After the first [C]PHNO scan, dextro-amphetamine (0.5 mg/kg, PO) will be given in increments of 5 or 10 mg, as it is available in 5 mg and 10 mg tablets, and will be rounded down to approximate 0.5 mg/kg total dose without exceeding it. Total dextro-amphetamine dose will not exceed 50 mg per scan. A second transmission and emission scan will be acquired approximately 2.5-3 hours post amphetamine identical to the methods outlined previously. The timing of the second [C]PHNO administration and subsequent PET scanning (i.e., 2.5-3 hours) corresponds to the time of maximum plasma concentration of amphetamine as stated in the respective FDA-approved product labeling. EKG and frequent BP monitoring will occur throughout the study and until the vital signs are within normal limits. Supplemental oxygen will be provided via nasal cannula if necessary. If the systolic BP reaches or exceeds 200 mmHg for more than 5 minutes, the study doctor will take the appropriate clinical measures in order to lower the BP, which may include phentolamine administration (5 mg IV over 10 min) or other appropriate measures.

Following the post-amphetamine PET scan, subjects will be assessed (EKG and vital signs) by one of the research nurses. Subjects will be discharged when vital signs are within normal limits and when behavioral changes (if any) are found to be not clinically significant by the MD attending to the subject at the PET Center. If subjects experience any adverse events, they will be treated until they become asymptomatic, prior to discharge.

Behavioral response to amphetamine will be measured by self-ratings with a simplified version of the Amphetamine Interview Rating Scale (van Kammen and Murphy, 1975). Four items will be investigated: euphoria ("feel good"), alertness ("feel energetic"), restlessness ("feel like moving") and anxiety ("feel anxious"). Self ratings will be obtained by analog scales at the following times relative to the d-amphetamine administration: -5 minutes, 0, and hourly thereafter until end of the second scan.

### **Cigarette challenges (same procedures as in protocol HIC 0804003655)**

Subjects will participate in one or more PET scans during which they will participate in 4 possible smoking challenges: Smoking an e-cig with no nicotine, an e-cig with a low dose of nicotine (6mg/mL-10mg/mL), an e-cig with a high dose of nicotine (24 mg/mL-36mg/mL), or smoking a regular cigarette. Subjects will participate in a different challenge for each of their PET scans. For the e-cig challenges, subjects will not be aware of the amount of nicotine in the e-cig. Subjects will abstain from smoking for ~1 week prior to each challenge day. After each PET scan, subjects will return to smoking for at least 1 week. They will then need to abstain from smoking for ~1 week prior to participating in their next PET scan. Because of this off-and-on smoking cessation, only non-treatment-seeking smokers will be asked to participate in this study. We have employed this procedure previously for protocol HIC 0804003655.

Use of e-cig: Based on the findings of a recent study that showed use of e-cigs led to similar plasma nicotine levels as tobacco smoking within 5 minutes of use, we plan to use an e-Go type e-cig battery (3.3 V, 1000 mAh) with 1.5 ohm dual-coil 510-style cartomizer and a 70/30 propylene glycol vegetable glycerin e-liquid with nicotine concentrations of approximately 0mg/mL, 6mg/mL-10mg/mL, and 24mg/mL-36mg/mL. Subjects will be instructed to puff on the e-cig once every 30 seconds in a manner as they normally would puff on a cigarette for 10 puffs total. A mouthpiece to measure puff topography may be used.

Use of regular cigarette: To standardize research methodology, Camels brand cigarettes will be used for all subjects. This brand is not prevalent with the smokers who participate in our studies and any subject who has used this brand prior will be excluded. Subjects will be instructed to

puff every 30 sec for a total of 10 puffs via the puff device (CreSS from Plowshare Technologies, USA), which provides measures of depth of puff inhalation and volume.

Blood Samples: On PET scan days, blood samples will be collected prior to radiotracer administration and at multiple time points after e-cig and tobacco cigarette use to determine nicotine concentrations in the blood, which will be assayed using reversed-phase HPLC .

## PET

PET scans may be performed on the High Resolution Research Tomograph (HRRT, 2-3 mm resolution) or another similar camera. Venous catheters will be used for i.v. administration of the radiotracers, venous blood sampling of AChE activity, for the administration of glycopyrrolate and physostigmine, and for venous blood sampling of physostigmine and amphetamine PKs. A radial artery catheter will be inserted by an experienced physician before the NCFHEB PET scans to draw arterial blood samples for metabolite analysis and for determination of the fraction of plasma radioactivity unbound to protein. At the beginning of scan, the subject's head will be immobilized and a transmission scan will be obtained for attenuation correction. PET scans will be acquired using bolus or bolus to infusion administration of up to 8 mCi of [F]NCFHEB or up to 10 mCi of [C]PHNO and subjects will be scanned for up to 4 hours. Dynamic images of radioactivity concentration are reconstructed with corrections for attenuation, normalization, random events, scatter, and deadtime. Subject motion is corrected automatically on an event-by-event basis with the Vicra motion tracking system. Vital signs (blood pressure, pulse and respiration) are collected prior to and during each PET scan. Urine pregnancy test will be again administered on the PET scan day prior to the initiation of any imaging procedures. Smoking abstinence, when appropriate, will also be confirmed for smoking subjects prior to PET scanning.

PET scanning will then proceed as following for each aim:

Aim 1. Subjects will be asked to come to the PET center on two separate days to participate in one NCFHEB PET scan each time to assess test retest reproducibility of binding parameters measured with the radiotracer.

**CLOSED** Aim 2. Subjects will participate in one NCFHEB PET scan day.

**CLOSED** Aim 3. Subjects from Aim 2 who are able to continue smoking abstinence will be asked to come back for another NCFHEB PET scan after about 4-8 weeks of smoking abstinence.

Aim 4. Baseline NCFHEB PET imaging will be conducted followed by administration of physostigmine. Preferably, this will be done on the same day. However, at times there is not enough radiotracer or subject is not able to tolerate a longer scan day. Therefore, some subjects may complete the study over two separate days (preferably within 1 month apart based on the availability of PET scanning times and subject's schedule).

**CLOSED** Aim 5. Baseline NCFHEB PET imaging will be conducted followed by administration of physostigmine. Preferably, this will be done on the same day. However, at times when there is not enough radiotracer or when a subject is not able to tolerate a longer scan day. Therefore, some subjects may complete the study over two separate days (preferably within 1 month apart based on the availability of PET scanning times and subject's schedule).

Aim 6. Subjects from Aim 4 may be asked to come back for another PET scan with physostigmine administration. Up to 8mCi of NCFHEB will be administered as a bolus plus constant infusion for the duration of the scan (up to 4 hours). Once equilibrium is reached (approximately two hours into the scan) glycopyrrolate and physostigmine will be administered and subjects will be scanned for approximately two more hours. A transmission scan will be acquired.

**CLOSED** Aim 7. Subjects from Aim 4 will be asked to come back for two [C]PHNO scans with amphetamine administration. Up to 10 mCi of PHNO will be administered. After the first scan, subjects will take amphetamine (0.5mg/kg) by mouth, and will be imaged again with PHNO. If technical difficulties arise the second PET scan will be scheduled as soon as possible (within 5 weeks). In that case, subjects may be asked to re-take amphetamine on the day of the rescheduled PHNO scan, approximately 3 hrs prior to the scan. Amphetamine dose will not exceed 50mg per scan. Subjects will not be allowed to drive home.

**CLOSED** Aim 8. Subjects who previously participated in Aim 4 or 6, or new subjects may complete this portion of the protocol as long as their yearly radiation dose allows. For Aim 8, subjects will participate in one or more PET scans during which they will participate in 4 possible smoking challenges: Smoking an e-cig with no nicotine, an e-cig with a low dose of nicotine (6mg/mL-10mg/mL), an e-cig with a high dose of nicotine (24 mg/mL-36mg/mL, or smoking a regular cigarette. Subjects will participate in a different challenge for each of their PET scans.. For each scan, up to 8mCi of NCFHEB will be administered as a bolus plus constant infusion for the duration of the scan (up to 4 hours). Once equilibrium is reached (approximately two hours into the scan), subjects will use a cigarette or e-cigarette (order will be predetermined ahead of time and subjects will be told what they will be using for each scan. However, if subjects are using the e-cig they will not be told which nicotine concentration they will receive). A transmission scan will be acquired.

Control subjects may participate in more than 1 aim. For example, nonsmoking subjects may complete Aim 1 and if they choose, participate in Aim 4. Thus, subjects may participate in up to 4 NCFHEB PET scans and up to 2 PHNO PET scans for this protocol per year. Subjects who complete 4 NCFHEB and 2 PHNO scans may return after 365 days to complete more scans under additional aims in this protocol.

### 3.6 Image analysis.

**NCFHEB** time activity curves will be extracted for each subject in the following brain regions: amygdala, caudate, cerebellum gray matter, cerebellum white matter, corpus callosum, anterior cingulate, posterior cingulate, frontal cortex, hippocampus, occipital cortex, pallidum, parietal cortex, putamen, temporal cortex, and thalamus. [name] and colleagues found that NCFHEB distribution volume ( $V_T$ ) can be estimated in humans using the one-tissue compartmental model. (139) We will perform and compare several quantification methods (such as one and two tissue compartment model, Logan, and multilinear analysis) on the test/retest dataset to define the optimal method for  $V_T$  derivation. The selected method will be used for the specific aims 2 studies.

$\beta_2$ -nAChRs are present in all brain regions, so that no practical region of reference can be used to define nonspecific binding. The definition of the nonspecific binding would require displacement studies, which are not proposed in this application. In the thalamus, where the density of B2-nAChR is the most abundant, the contribution of nonspecific binding to the total NCFHEB  $V_T$  is

small in rhesus monkey (20%) (unpublished data), so that significant changes in thalamic NCFHEB VT can be reasonably ascribed to changes in specific binding. In other regions such as cortex, the contribution of the nonspecific binding to VT is larger (about 60%, unpublished data), thus global VT changes in these regions should be interpreted carefully.

For **PHNO** scans, The primary outcome measure is the binding potential ( $BP_{ND}$ ), which in turn is proportional to the available receptor concentration ( $B_{avail}$ ), given that there is no change in affinity ( $K_D$ ) and that nondisplaceable (nonspecific and free) uptake does not differ between subjects and studies. We will examine the regions-of-interest listed below with the cerebellum used as a reference region because it is devoid of  $D_{2/3}$  receptors.

We obtain an MRI (as previously described) to use as a guide to place our regions of interest. This is because we can define anatomical regions of interest on the MRI, which provides structural information and then we can apply these regions of interest to the PET scans. The PET scans alone are not sufficient to identify brain regions. The PET image sets are aligned and resliced to yield images in the same planes and spatial system as the MRI images using AAL template. Primary ROIs will be caudate, putamen, globus pallidus, substantia nigra, midbrain, thalamus, hippocampus, cingulate, frontal and occipital cortices, as well as raphe and amygdala. Other ROIs will be examined *post hoc* to assess radiotracer binding. Cerebellum will be the reference region.

### 3.7 Statistical analysis.

**3.7 a Power Analysis in Never Smokers:** Assuming Hardy-Weinberg equilibrium, the allele frequency predicts that 30 will be homozygous (CC); 25 will be heterozygous (CT) and 5 will be homozygous (TT) for the ANKK1 alleles, and 11 will be homozygous (AA) 29 will be heterozygous (AG) and 20 will be homozygous (GG) for the CHRNA5 alleles. In a one-way ANOVA analysis, sample sizes of 30, 25, and 5 are obtained from the three genotypes of ANKK1 whose means are to be compared. The total sample of 30 subjects achieves 0.96 power to detect differences among the means versus the alternative of equal means using an F test with a 0.05 significance level for thalamus. The size of the variation in the means is represented by their standard deviation which is 17.49. The common standard deviation within a group is assumed to be 32.30. The other powers are 0.95, 0.87, and 0.99 for ANKK1 for the brain regions of striatum, cerebellum and cortex, respectively. We have enough power to detect the effect with the proposed sample size. We aim to recruit at least 10 subjects that are homozygous for TT; if we do not achieve our goals for the rarer genotype by the end of year 3; we will screen subjects prior to imaging them in year 4.

**3.7.b Power Analysis in Smokers:** The group means of  $\alpha_2$ -nAChR availability for the heterozygotes of hCV16178933/rs2273504 or hCV15953820/rs2236196 are higher in smokers than non-smokers in the brain regions of striatum, cerebellum and mean cortex, but not thalamus. We can achieve 0.81 power to detect a difference of 11.7 in striatum between the null hypothesis that both group means are 97.5 and the alternative hypothesis that the mean of non-smoking group is 85.8 with estimated group standard deviations of 14.9 and 10.8 and with a significance level (alpha) of 0.05000 using a one-sided two-sample t-test for hCV16178933/rs2273504. The other powers are 0.97, 0.95 for hCV16178933/rs2273504 and for cerebellum and mean cortex, respectively. The differences do not present in the homozygote subjects. We can also achieve 0.98 to 0.99 for hCV15953820/rs2236196 in the brain regions of striatum, cerebellum and mean cortex.

Genotype quality control – genotyping error and missing genotype We will check the genotypes for the SNPs via the method of departures from Hardy-Weinberg equilibrium (HWE) developed by (157), and excluded genotyping errors as a likely cause of the disequilibrium. Genotyping errors and missing genotype/allele calls will be carefully examined. Those with genotyping errors will be assigned to be missing.

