This innovative paradigm will lay the groundwork for future studies that can directly interrogate ACh function in the living human brain. This is critical to the advancement of our understanding of ACh involvement in psychiatric and medical disorders.

Additionally, a substantial literature body demonstrates that nAChRs and the cholinergic system dynamically control the mesolimbic DA system by enhancing, inhibiting, and filtering striatal DA release. We have preliminary data suggesting tobacco smokers at 2 weeks of abstinence have blunted DA release compared to nonsmokers. We propose in Aim 7 to determine 1)

whether there is reduced DA release in smokers at 2 weeks of withdrawal vs. nonsmokers, 2) if the magnitude of DA release is correlated with alterations in ACh levels measured in Aim 4 and 3) if alterations in DA and ACh predict relapse vulnerability.

**Aim 1: To determine the test-retest reproducibility of NCFHEB binding parameters in 10 nonsmoking subjects.**  $\beta_2$ -nAChRs will be quantified twice in nonsmoking subjects. Based on preclinical evidence, we hypothesize within 20% difference of binding parameters between test and retest scans.

**CLOSED Aim 2: To determine if  $\beta_2$ -nAChR availability is genetically predisposed in never smokers and smokers** We propose to determine if the ANKK1 genotype (rs4938015/hCV38879) or CHRNA4 genotype determines  $\beta_2$ -nAChR availability in adult never smokers. Specifically, 10 never smokers and 10 smokers at one week of abstinence will be imaged using NCFHEB PET and blood samples for DNA extraction will be collected from all subjects.

**Hypothesis:** Homozygotes (TT) will have higher  $\beta_2$ -nAChR availability compared to age-, and sex matched heterozygotes that carry the C allele in the ANKK1 gene (rs4938015/ hCV38879).

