**Never Smokers:** In a one-way ANOVA analysis, sample sizes of 30, 25, and 5 are obtained from the three genotypes of ANKK1 whose means are to be compared. The total sample of 30 subjects achieves 0.96 power to detect differences among the means versus the alternative of equal means using an F test with a 0.05 significance level for thalamus. The size of the variation in the means

is represented by their standard deviation which is 17.49. The common standard deviation within a group is assumed to be 32.30. The other powers are 0.95, 0.87, and 0.99 for ANKK1 for the brain regions of striatum, cerebellum and cortex, respectively. We have enough power to detect the effect with the proposed sample size. We aim to recruit at least 10 subjects that are homozygous for TT; if we do not achieve our goals for the rarer genotype by the end of year 3; we will screen subjects prior to imaging them in year 4.

**Smokers:** The group means of  $b_2$ -nAChR availability for the heterozygotes of hCV16178933/rs2273504 or hCV15953820/rs2236196 are higher in smokers than non-smokers in the brain regions of striatum, cerebellum and mean cortex, but not thalamus. We can achieve 0.81 power to detect a difference of 11.7 in striatum between the null hypothesis that both group means are 97.5 and the alternative hypothesis that the mean of non-smoking group is 85.8 with estimated group standard deviations of 14.9 and 10.8 and with a significance level (alpha) of 0.05000 using a one-sided two-sample t-test for hCV16178933/rs2273504. The other powers are 0.97, 0.95 for hCV16178933/rs2273504 and for cerebellum and mean cortex, respectively. The differences do not present in the homozygote subjects. We can also achieve 0.98 to 0.99 for hCV15953820/rs2236196 in the brain regions of striatum, cerebellum and mean cortex.

Genotype quality control – genotyping error and missing genotype We will check the genotypes for the SNPs via the method of departures from Hardy-Weinberg equilibrium (HWE) developed by (157), and excluded genotyping errors as a likely cause of the disequilibrium. Genotyping errors and missing genotype/allele calls will be carefully examined. Those with genotyping errors will be assigned to be missing.

SECTION III: RESEARCH INVOLVING DRUGS, BIOLOGICS, RADIOTRACERS, PLACEBOS AND DEVICES

--

*If this section (or one of its parts, A or B) is not applicable, state N/A and delete the rest of the section.*

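### Aim 2 (ANKK1) hypothesises TT above heterozygotes, but the only test and power given are for a three-genotype omnibus F test, so the 0.96 is not the power for that comparison

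*Combined protocol and SAP*

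**What the plan says.** All references are to the NCFHEB protocol, the first of the two protocols in the combined file.

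- **Hypothesis** (Section II, item 1, Aim 2): "Homozygotes (TT) will have higher" receptor availability "compared to age-, and sex matched heterozygotes that carry the C allele in the ANKK1 gene". This is one pair of genotypes with a stated direction. The aim itself is broader: whether the ANKK1 or CHRNA4 genotype determines availability.
- **Expected genotypes** (3.7 a): "30 will be homozygous (CC); 25 will be heterozygous (CT) and 5 will be homozygous (TT) for the ANKK1 alleles".
- **Test and power** (3.7 a, repeated in item 12, Never Smokers): a one-way ANOVA in which "sample sizes of 30, 25, and 5 are obtained from the three genotypes of ANKK1 whose means are to be compared", and which "achieves 0.96 power to detect differences among the means versus the alternative of equal means using an F test" at the 0.05 level for thalamus. The SD of the means is 17.49 and the within-group SD is 32.30. Power for striatum, cerebellum and cortex is 0.95, 0.87 and 0.99. The text concludes that power is sufficient for the effect.
- **TT target** (same places): at least 10 TT subjects, with genotype screening before imaging in year 4 if the target is not met by the end of year 3.
- **Aim 2 status and size** (Section II, item 1, and 3.1): marked closed; 10 never smokers and 10 smokers.

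No TT-versus-CT contrast, direction of test or follow-up procedure is given for ANKK1. The one-sided t-test in 3.7.b compares smokers with non-smokers among heterozygotes of other SNPs. The multiple-comparison wording in the file belongs to the separate PHNO protocol.

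**The concern.** The F test's null is that CC, CT and TT have equal means. The hypothesis concerns TT and CT only, and only one direction. A significant F can arise because CC differs while TT and CT are the same, or because TT is lower. A true TT excess over CT can also go undetected in the pairwise comparison, because only 5 TT subjects are expected. At stake are two things: whether an ANKK1 result can be tied to the stated hypothesis, and whether the stated sufficiency of power describes the effect that was hypothesised.

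**Working it through.** **Inputs.** From 3.7 a and item 12: group sizes 30/25/5, SD of means 17.49, within-group SD 32.30, alpha 0.05. No genotype means are given, so the patterns below are assumptions, each scaled to the plan's own SD of means.

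**1. Reproduce 0.96.**
- f = 17.49/32.30 = 0.5415.
- λ = N·f² = 60 × 0.5415² = 17.59, df (2, 57). Power = 0.964, matching 0.96.
- The text says "The total sample of 30 subjects achieves 0.96 power to detect differences among the means versus the alternative of equal means", but 30 + 25 + 5 = 60. With N = 30, power would be 0.71, so the 0.96 belongs to 60 subjects.
- The match uses the SD of means weighted by group size. With that SD fixed, λ is the same for every pattern of means. The 0.96 therefore says nothing specific about TT versus CT.

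**2. TT = CT, only CC differs.**
- CC is half the sample, so weighted SD = shift × √(0.5 × 0.5) and shift = 17.49/0.5 = 34.98. In SD units, 34.98/32.30 = 1.08.
- F rejects with probability 0.964. A TT-minus-CT contrast rejects at its nominal 0.05.
- For smaller shifts, λ = 60 × 0.25 × (shift in SD)². At 0.5 SD, λ = 3.75 and F rejects 37%; at 0.25 SD, 12%; at 0.75 SD, 72%.

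**3. Additive pattern (hypothesis true).**
- In allele steps 0/1/2, the mean is (25 + 10)/60 = 0.583. The variance is (25 + 20)/60 − 0.583² = 0.410 and the SD 0.640.
- Step = 17.49/0.640 = 27.3, which is TT − CT.
- With 5 TT: SE = 32.30 × √(1/25 + 1/5) = 15.8; noncentrality 27.3/15.8 = 1.73; df 57. Power is 0.40 two-sided and 0.52 one-sided. F power stays at 0.964.
- With 10 TT and the same difference: SE = 32.30 × √(1/25 + 1/10) = 12.1; noncentrality 2.26; df 62. Power is 0.60 two-sided and 0.72 one-sided.

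**4. Only TT raised.** Weighted SD = shift × √(5/60 × 55/60) = 0.276 × shift, so shift = 63.3 (1.96 SD). Contrast power with 5 TT is 0.98.

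**5. At the size Aim 2 states.**
- Ten never smokers at the plan's proportions give about 5 CC, 4 CT and 1 TT.
- SE = 32.30 × √(1/4 + 1/1) = 36.1, df 7. Two-sided contrast power is about 0.10 (additive, 27.3) and 0.33 (TT only, 63.3).
- If subjects are not selected by genotype, the chance of imaging no TT subject is (55/60)¹⁰ = 0.42.

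**The case against.** Five points can fairly be made for the plan.

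- **The F test fits the aim as worded.** Aim 2 also asks whether genotype determines availability, and a three-genotype F test addresses that. This stands: the F test is not misplaced and need not be demoted. It does not answer the narrower hypothesis written beneath the aim.
- **The 96% needs a large CC shift.** This also stands. A reader might infer that F nearly always rejects when TT equals CT. It does so only at the plan's full SD of means; at 0.5 SD the figure is 37%. The 96% shows what the 0.96 measures and is not a forecast of a false claim.
- **The plan enriches for TT.** Using 5 TT throughout would ignore the target of at least 10. With 10, contrast power under the additive pattern rises to about 0.60, still well below 0.96. The 42% chance of no TT subject applies only to unselected sampling.
- **Direction would be visible in the means.** A reader might infer that any significant F would be reported as support for TT above CT. The documents do not say so, and reported genotype means would show a reversal. The gap is that no test or interval for that comparison is planned.
- **Aim 2 is closed.** New prospective power wording then has limited use. The analysis text still stands in two places and governs how the data are reported.

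**Conclusion.** The ANKK1 hypothesis has no matching test or power in the NCFHEB protocol. The 0.96 is correct as omnibus power for 60 subjects at a weighted SD of means of 17.49, but it does not measure power for TT above CT. Under an additive pattern at that SD, pairwise power is about 0.40 two-sided with 5 TT and 0.60 with 10, so the statement of sufficient power does not hold for the hypothesised effect in general.

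This rests on the weighted reading of 17.49, which reproduces 0.96, and on assumed patterns of means. It is tempting to read 0.40 to 0.98 as the contrast's power range. The documents do not support that: the ends come from chosen patterns, the upper one needs TT to be 1.96 SD above both other groups, and both use 25 CT and 5 TT, whereas Aim 2 images 10 never smokers.

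The correction is worth making, but it is limited to analysis and reporting of a closed aim.

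**What to change.** In 3.7 a and item 12:

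1. Keep the three-genotype F test for the general question of whether ANKK1 genotype matters.
2. Add one planned contrast, TT minus heterozygotes, using the ANOVA error term and reported with a 95% CI, as the test of the stated hypothesis.
3. Label 0.96 as omnibus power for 60 subjects, and withdraw the claim of enough power for TT versus CT.
4. Give any contrast power or precision for the TT and CT numbers actually imaged, stating the assumed pattern of means. The 25 CT/5 TT figures should not be carried over.
5. State that the hypothesis is not evaluable if no TT subject is imaged.
6. Because Aim 2 is closed, apply this to the analysis and report, and label the contrast post hoc if the data have already been seen.

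The cost is wording in two places and one contrast in the same model, with no new subjects or scans. The stated power for the hypothesis becomes less favourable.
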